#### 9.3 Adverse Event Reporting:

Investigators will be responsible for reporting the following pre-defined adverse events regardless of severity, to Tactile Medical in a timely manner:

- New or worsening ulceration

- Clinically worsened or new onset heart failure
- Increase in leg swelling greater than 20%
- Skin irritation/blistering
- Infection of the study limb(s)
- Other – an AE that according to the investigator’s opinion is significant and requires reporting to Tactile Medical but doesn’t necessarily meet the definition of the pre-defined AEs or an SAE

**10.0 Deviation from Investigational Protocol:**

Any deviation from this protocol undertaken to protect the life or physical well-being of a subject in an emergency situation must be reported to Tactile Medical and the respective IRB as soon as possible, but in no event later than five (5) working days after the emergency occurred. Anticipated deviations from the protocol in a non-emergency situation must be pre-approved by Tactile Medical via telephone, email, fax, or mail. It is preferred that deviations scheduled to be performed in a nonemergency situation not be conducted until authorized by Tactile Medical. All protocol deviations must be documented. Deviation that may affect the scientific soundness of the study, or the rights, safety or welfare of the subject must also be reported to the reviewing IRB according to their reporting requirements. Protocol deviations may necessitate the discontinuation of the subject or the investigational site from the study.

**11.0 Quality Assurance Procedures:**

This study will be conducted in accordance with Good Clinical Practice and International Conference on Harmonization (ICH) Guidelines, Code of Federal Regulations (CFR), institutional research policies and procedures and other appropriate regulatory requirements to ensure subject safety and quality of clinical procedures related to the conduct of the clinical trial. The investigators will permit regular monitoring, audits and site inspections by the IRB, the sponsor, government regulatory bodies and any institution compliance and quality assurance groups of all study related documents (e.g. source documents, regulatory documents, data collection instruments, study data, etc.). The investigator will ensure the capability for inspection of applicable study related facilities. Clinical trial monitoring may be conducted to ensure compliance to this protocol.

11.1 Site Qualifications:

Tactile Medical may conduct onsite visits or telephone qualification (pre-study audit) prior to study initiation to verify adequate resources, qualified staffing and a sufficient subject pool.

11.2 Data Collection Procedures:

Raw data will be collected on appropriate Source Document Worksheets, or site-specific appropriate forms which include but are not limited to, clinic charts and site-generated Source Document Worksheets. Data collected shall be entered into the validated and secure Clindex electronic data capture system.

11.3 Clinical Site Monitoring:

Clinical sites will be monitored for compliance with the clinical protocol, investigator agreement, and applicable regulatory requirements. Regular contact will be maintained to ensure:

- Subject safety
- That clinical site staff is well informed of regulations and sponsor requirements
- That the clinical protocol is followed
- That data is gathered in a complete and timely way
- That problems with data or data collection are addressed appropriately and in a timely manner
- That adverse events are properly reported in a timely manner

Investigator and Institution will permit trial related monitoring, audits, IRB review, and regulatory inspection(s), providing direct access to source data and documents as appropriate. Monitoring will be performed by study sponsor and/or designee. Monitoring will review subject source documentation and Case Report Forms (CRFs) for accuracy, completeness, and compliance with Good Clinical Practice procedures. In addition to site visits, a screening log will be submitted to Sponsor or designee by the sites as requested (by fax or e-mail). This screening log will be reviewed with the site for plan vs. actual recruitment purposes.

#### 11.4 Data Safety Monitoring Board:

An independent data safety monitoring board (DSMB) will be established by the sponsor to review and monitor any serious adverse events, review safety data and may be called upon to review interim analysis data. The frequency of the review is expected to be quarterly but may be dependent on a number of parameters including but not limited to; the rate of enrollment, number of AEs and/or SAE, number of significant deviations from the protocol. At the conclusion of the review the DSMB may provide recommendations pertaining to study continuation, modification, or termination of the trial or a specific investigational site.

#### 11.5 Investigator Reports and Records:

Records to be maintained by the investigator in a designated study file include:

- Investigational plan and all amendments
- Signed Investigator Agreement
- IRB approval letter, including a copy of the approved consent forms, progress reports, Adverse Event Report
- IRB roster or Assurance number, if applicable
- All correspondences relating to the conduct of this study between the site and sponsor, IRBs, and study monitor
- Curriculum Vitae and professional license for all study personnel, if applicable
- Site personnel signature and documentation regarding the Investigator's delegation of responsibility
- Clinical Site Visit log

- Protocol/device related training records for all applicable study personnel
- Investigational device inventory information including the date, quantity and serial number of all devices and received identification of all subjects who received treatment, and final disposition of the devices.
- Screening log
- Reports (see Table 3)

The following records must be maintained for each subject enrolled:

- Signed and dated informed consent form
- Completed CRFs, queries and source document worksheets (if applicable)
- Complete medical records including procedure reports, lab reports (if applicable), etc.

Investigators are required to prepare and submit to the sponsor or its designees complete accurate and timely reports on this investigation as required by regulations. The types of reports to be submitted are summarized in Table 3.

**Table 3: Investigator Reports**

Reports	Submit To	Timeframe
Unanticipated Adverse Device Event	Sponsor and Reviewing IRB DSMB	As soon as possible but no later than 10 working days
Withdrawal of IRB Approval	Sponsor	Within 5 working days
Progress	Sponsor and Reviewing IRB	Annually, at a minimum
Final	Sponsor and Reviewing IRB	Within 3 months following the completion or termination of the Investigator's part

Subject study records, correspondence files, all supporting study documentation, and reports must remain on file at the investigational site for a minimum of ten years after the conclusion of this study. All investigators must contact Tactile Medical prior to destroying or archiving off-site any records and reports pertaining to this study to ensure that they no longer need to be retained on-site.

Additionally, Tactile Medical must be contacted if the Investigator plans to leave the investigational site to ensure that arrangements for a new Investigator or records transfer are made prior to the Investigator's departure.

**11.6 Change to Study Plan:**

Should changes in the study plan or protocol become necessary in the course of the clinical trial, those specific changes will be discussed and agreed upon by the Sponsor, its acting representative if appropriate, Investigator, and appropriate IRB

approval obtained before the changes are implemented. All changes must be documented.

## 12.0 Data Analysis and Statistical Considerations

### 12.1 Statistical Considerations:

This is a prospective, randomized, stratified, open label, parallel-group, multi-center trial designed to assess the clinical non-inferiority with respect to the percentage of wound area reduction at 16 weeks with the ACTitouch® Adaptive Compression System compared to the Multi-layer Bandaging system in subjects with venous leg ulcer (VLU). Secondary endpoints include health-related quality of life (HRQOL) and Cost of the ACTitouch® Adaptive Compression System compared to the Multi-layer Bandaging system in subjects with VLU. Two hundred and four (204) subjects will be randomized 1:1 into 2 arms, ACTitouch® and Multi-layer Bandaging Systems. Subjects will receive follow-up evaluations at regularly scheduled clinic visits during 16 weeks of follow-up. Subjects will be randomized to 4 strata based on ulcer size and duration (age):

- Size of Ulcer
  - $1.5\text{cm} \leq \text{size} \leq 12\text{cm}$
  - $12\text{cm} < \text{size} \leq 50\text{cm}$
- Age of Ulcer
  - $1 \leq \text{age} \leq 6$  months
  - $6 < \text{age} \leq 24$  months

Subjects will be randomized to treatment groups within strata using a web-based randomization process.

Unless otherwise specified, all safety data, efficacy data, demographic data, and other baseline characteristics will be summarized by treatment group. Continuous data will be summarized by reporting the number of observations, mean, standard deviation, median, minimum and maximum values. Categorical data will be described using frequency tables showing the number and percentage of subjects falling within a particular category.

Efficacy analysis and associated p-value calculation are described below and will be further elaborated in the Statistical Analysis Plan (SAP) issued prior to database lock. Statistical tests will be performed at a one-sided alpha of .025 for non-inferiority and two-sided alpha level of 0.05 for all other comparisons, unless otherwise specified. Between-group analyses will employ analysis of covariance (ANCOVA) with stratum and treatment group as covariates for continuous data, and chi-square or Cochran-Mantel Haenzel (CMH) methods for stratified categorical data. Kruskal-Wallis tests will be used to compare ordinal variables stratified by ulcer age, wound area and treatment group. If serious departures in the assumptions of normality and homogeneity of variance occur, nonparametric methods will be used for continuous data.

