**6.0 Study Visit Summaries:**

6.1 Screening Visit:

At this visit, the patient will be asked to provide written informed consent and inclusion and exclusion criteria will be evaluated to ensure that the patient meets all entrance criteria. See the Study Schedule of Activities section 7.17 for visit activities. After the informed consent process is complete, the subject will begin the run-in phase of the study.

Subjects may be enrolled if they are on a current Pentoxifylline regimen, but Investigators should not start patients on Pentoxifylline during the trial if the patient is not taking the drug at enrollment.

6.2 Run-in Visit:

There could be up to 4 visits during the run in phase, 3 visits if the Screening and Baseline visits occur on the same day. The visit schedule is as follows Screening/Baseline; Run-in Week 1 and Randomization ( $\pm 2$  days). The subjects will follow the treatment regimen outlined in section 7.17. At each visit the study staff will access the ulcer. If the subject meets any of the exclusion criteria listed in section 5.2.3 at the Randomization Visit the subject will be excluded from the study.

6.3 Randomization Visit:

At the randomization visit the subject will undergo procedures as outlined in the Study Schedule of Activities table in section 7.17.

The subject will leave the randomization visit with:

- Schedule for the next study visit (if possible, follow-up visits should be scheduled at the same time of day)
- Instructions on use and application of the assigned study apparatus, as applicable
- Diary and instructions to record daily activity
- Contact information and instructions to call if any problems arise

6.4 Treatment Visits (Weeks 1-16 or healed):

Investigational Group: Subjects will be seen in clinic at weeks 1, 2, 4, 6, 9, 12, 16 ( $\pm 2$  days) for 16 weeks or until the VLU is completely healed, as defined by complete closure with no open area or exudate. At the visits the subject will undergo the procedures as outlined in the Study Schedule of Activities table in section 7.17.

Control Group: Subjects will complete weekly visits for 16 weeks or until the VLU is completely healed, as defined by above. At the weekly visits the subject will undergo procedures as outlined in the Study Schedule of Activities table in section 7.17.

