### 12.3 Endpoints:

#### 12.3.1 Primary Endpoints

The percentage of ulcer area reduction at 16 weeks.

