#### 12.6.2 Primary Endpoint Analysis:

The percentage of each subject's ulcer area reduction at 16 weeks will be assessed using a specialized ulcer camera and ulcer imaging system. Images will be centrally read by a qualified independent adjudicator. The percentage of ulcer area reduction for the ACTitouch® treated subjects will be compared with multi-layer bandaging treated subjects using analysis of covariance (ANOCOVA) with the following covariates: treatment group; duration of VLU ([1,6]; (6,24] months); baseline size of VLU, [1.5,12cm], (12,50cm]; history of diabetes; age. The analysis will be conducted on the ITT, MITT and Completer populations. The covariate adjusted one-sided lower bound 97.5% confidence interval of the treatment difference in mean percent ulcer area reduction (calculated as mean of ACTitouch® group minus mean of multi-layer bandaging treated group) is compared to the non-inferiority margin (-.125). If the lower bound exceeds the margin, the null hypothesis is rejected, and ACTitouch® system is deemed non-inferior to multi-layer bandaging.

A treatment-by-study center interaction will be assessed at the 0.10 level of significance using analysis of covariance with effects for treatment, study center and treatment-by-study center interaction. A non-significant interaction or any significant interaction deemed only quantitative in nature will not preclude study centers from being pooled for the final analysis. A significant qualitative interaction will be further inspected to

assess the study centers causing the interaction. Study centers with less than 15 subjects will be pooled by geographic region prior to carrying out the analysis.

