#### 12.7 Interim Analysis:

There will be a formal interim analysis of the primary endpoint when 50% of the subjects have completed the 16 week treatment phase, defined as completing all 16 weeks, healed or withdrew prior to the 16 week visit or healing. At this interim visit, comparison of the percentage ulcer area reduction between ACTitouch® treated subjects with multi-layer bandaging treated subjects will be made using the same ANOCOVA model as above. The DSMB will not recommend stopping the study for overwhelming efficacy based on the comparison of the ACTitouch® doses versus control (multi-layer bandaging). Nevertheless, due to the interim look, an O'Brien-Fleming-type alpha-penalty for the final analysis will be taken; and the final one-sided alpha will be 0.0249

The DSMB will be provided with conditional power of obtaining non-inferiority of ACTitouch to control with respect to mean percent ulcer healing by the end of the study. This conditional power is calculated according to the following formula:

$$CP_{\delta}(n_2, Z_{\alpha}|Z_1) = 1 - \Phi \left[ \frac{Z_{\alpha} \sqrt{2(n_1+n_2)} - Z_1 \sqrt{2n_1} - n_2(\delta - \delta_{\Delta})}{\sqrt{2n_2}} \right]$$

where:

$n_1$  – sample size per arm at interim;

$n_2$  – sample size per arm in second stage (from interim to final analysis) as originally planned;

$\Delta$  – non-inferiority margin;

$\delta_{\Delta} = \Delta/\sigma$  ;

$\sigma^2$  – assumption of true variance of treatment effects pooled across arms (estimated from the interim data);  
 $\delta$  – assumption of true effect size= $(\mu_C - \mu_T)/\sigma$  (this will be set to 0);  
 $z_1$  – non-inferiority test statistic calculated at the interim analysis;  
 $z_\alpha$  –  $\alpha$  percentile of the standard normal distribution ( $\alpha =$  one-sided 0.0249);  
 $z_\beta$  –  $\beta$  percentile of the standard normal distribution;  
 $\Phi[\ ]$  – the standard normal cumulative distribution function.

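### Section 12.1's undefined switch to nonparametric methods reaches the primary endpoint as worded, while the only non-inferiority margin is a mean difference, and nothing says which text prevails

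*Protocol*

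**What the plan says.** Protocol 12.1 sets defaults for the efficacy analyses. It fixes the level ("Statistical tests will be performed at a one-sided alpha of .025 for non-inferiority"), names ANCOVA for between-group comparison of continuous data, and then adds the fallback: "If serious departures in the assumptions of normality and homogeneity of variance occur, nonparametric methods will be used for continuous data". It defines neither what counts as a serious departure nor how it is to be detected, who decides, or which nonparametric method follows.

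The primary endpoint is continuous: "The percentage of ulcer area reduction at 16 weeks". Section 12.6.2 compares ACTitouch with "multi-layer bandaging treated subjects using analysis of covariance (ANOCOVA) with the following covariates: treatment group", ulcer duration class, baseline size class, diabetes history and age. The decision rests on the lower 97.5% bound of the "treatment difference in mean percent ulcer area reduction (calculated as mean of ACTitouch® group minus mean of multi-layer bandaging treated group"), which "is compared to the non-inferiority margin (-.125"). After the interim look, section 12.7 states that "the final one-sided alpha will be 0.0249".

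SAP 8.3.1 specifies a linear mixed model ANCOVA with the same covariates, and the note to SAP Table 14.2.3 repeats the mean-difference rule and margin. Neither has a nonparametric branch for this endpoint. Where the documents want such a method they name it: Wilcoxon tests for costs and nonparametric ANCOVA for ulcer-free days. The sensitivity analyses at the end of 12.6.2 concern missing data only.

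**The concern.** Percentage area reduction cannot exceed 100%, and subjects are treated "for 16 weeks or until the VLU is completely healed, as defined by complete closure with no open area or exudate", so every healed ulcer takes the same value at the top of the scale. The condition that opens the fallback is therefore foreseeable, while the choice to use it would be made after the data are seen, in an open-label trial.

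If the fallback were applied with a rank method, the result would no longer estimate the mean difference to which the margin belongs, and no margin on a rank or location-shift scale is given. Two consequences follow. The primary result gates the secondary tests (12.6.1), so an invalid verdict would carry forward. The interim analysis (12.7) uses the ANCOVA model and a conditional power built on the margin divided by the standard deviation, so a rank-based final test would not match the quantity that was monitored.

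**Working it through.** **1. What can be reproduced.** The planned size is 204, or 102 per arm. The SD, power, assumed difference and dropout are not visible in the public copy, so the sample size cannot be reproduced. The SD it implies can be solved for, at one-sided 0.025, margin 0.125, true difference 0 and no dropout:

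SD = 0.125 / (z₀.₉₇₅ + z_power) × √(102/2)

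- 80% power: 0.125 / (1.960 + 0.842) × 7.141 = 0.319
- 90% power: 0.125 / (1.960 + 1.282) × 7.141 = 0.275

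**2. Assumed outcome shape.** The documents give no healing rate and no distribution for unhealed ulcers. Assumed here: a share h of each arm sits at exactly 1.0 (healed), and the rest follow -0.5 + 1.5 × Beta(3, 1.6), with mean -0.5 + 1.5 × 3/4.6 = 0.478. The resulting SD is 0.29 to 0.35 for h from 20% to 70%, which overlaps the implied range. There is no covariate adjustment.

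**3. Would the assumptions look violated?** For h from 20% to 70%, Shapiro-Wilk on the residuals rejected normality in 100% of runs. Levene's test rejected equal variances in 4% to 6% of runs when the arms did not differ. In a repeat of the simulation with a true mean difference of -0.125, it rejected in 5% to 81%, depending on scenario.

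**4. Error rate at the margin.** The true mean difference is set to -0.125 in two ways:

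- Healing-rate deficit: the ACTitouch healing share is h - 0.125/(1 - 0.478) = h - 0.240.
- Non-healer deficit: equal healing, with ACTitouch non-healers shifted down by 0.125/(1 - h), for example 0.25 at h = 50%.

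Two lower bounds are set against -0.125: the t bound for the mean difference, and the bound from inverting the Wilcoxon test (Hodges-Lehmann). Entries are the percentage of trials that falsely declare non-inferiority; nominal is 2.5%.

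| Control healed | Mean, healing deficit | Rank, healing deficit | Mean, non-healer deficit | Rank, non-healer deficit |
|---|---|---|---|---|
| 30% | 2.7 | 1.5 | 2.6 | 7.3 |
| 40% | 2.0 | 2.3 | 2.6 | 26.3 |
| 50% | 2.5 | 7.7 | 2.7 | 64.2 |
| 60% | 2.5 | 24.8 | 2.3 | 95.8 |
| 70% | 2.5 | 59.1 | 3.5 | 99.8 |

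There were 4,000 runs for the mean test under the healing deficit and 1,500 for each other column. The Monte Carlo standard error at 2.5% with 1,500 runs is √(0.025 × 0.975/1500) = 0.4 points. A repeat of the simulation gave about 2% to 3.5% for the mean-based test, and 1% to 60% and 9% to 100% for the two rank columns.

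**5. Why the rank bound drifts.** The Hodges-Lehmann estimate is the median of the 102 × 102 = 10,404 pairwise differences. With a true mean difference of -0.125 it ran from -0.139 (30% healed) to -0.012 (70%) under the healing deficit, and was 0.000 at 60% to 70% under the non-healer deficit.

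One part of this needs no assumed shape. The lower bound lies just above the k-th smallest difference, with k = 10,404/2 - 1.96 × √(10,404 × 205/12) = 5,202 - 826 ≈ 4,375. A difference can be negative only if the ACTitouch subject is unhealed. With 60 of 102 ACTitouch subjects healed, at most 42 × 102 = 4,284 differences are negative, fewer than 4,375. The bound is then zero or above and clears -0.125, however badly the non-healers do.

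**The case against.** The strongest reply is that specific text overrides general text. Section 12.1 announces itself as a set of defaults to be elaborated. Its default ANCOVA has only stratum and treatment as terms, and 12.6.2 visibly replaces that with five terms, a mean-difference bound and a margin. The SAP fixes one model and one table, and names nonparametric methods only where it wants them. An analyst could fairly conclude that the fallback never reaches the primary test. This reading is reasonable, but the documents do not settle it: a fallback exists to modify a named default, so naming ANCOVA does not by itself disable it. The SAP supplied is an abbreviated one that refers to an original SAP not provided. That fuller version may define the clause; nothing at hand does.

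Three stronger readings are tempting and are not supported:

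- **That the switch will be triggered.** A serious departure is undefined, no diagnostic is named, and the wording joins normality with homogeneity of variance. Rejection by Shapiro-Wilk is not the plan's criterion. Equally, the joint wording does not reliably block the switch, since variances can differ as well when the arms differ.
- **That any nonparametric result is incompatible with the margin.** A bootstrap or permutation interval for the mean difference is nonparametric and can be set directly against -0.125. Even a Hodges-Lehmann bound can be placed beside that number; the difficulty is that it estimates something else.
- **That the planned mean-based test is unsound for capped data.** The simulation shows the opposite at about 100 per arm.

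It is also fair to say that the large error rates belong to one unadjusted rank rule that the plan never names for this endpoint, under assumed shapes.

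**Conclusion.** The point holds as an unresolved conflict between a general rule and the primary analysis, not as a demonstrated error in the primary test. As worded, 12.1 permits a data-dependent change of primary method with no stated trigger, and one natural way of applying it has no valid margin.

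The size depends on how the clause is applied and on where any deficit lies. There is no inflation at 30% to 40% control healing with a healing-rate deficit (1.5% to 2.3%). False non-inferiority is 7.7% to 59% at 50% to 70% healing with that deficit, and 7% to 99.8% when the non-healers do worse. The ANCOVA-type comparison of means stayed at 2.0% to 3.5%, so for this endpoint the fallback solves no problem that the simulation could find.

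These figures rest on the assumed healing rates and non-healer shape, no covariates, no dropout, and 0.025 in place of 0.0249. The result for 60 or more healed of 102 rests only on the Wilcoxon large-sample bound without tie correction.

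**What to change.** Add one sentence to Protocol 12.1, mirrored in SAP 8.3.1: the nonparametric fallback does not apply to the primary non-inferiority test, which always rests on the covariate-adjusted mean difference and margin defined in 12.6.2 and SAP 8.3.1; any rank-based analysis of this endpoint is supportive only.

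A heteroscedasticity-robust or stratified bootstrap bound for the mean difference may be listed as a sensitivity check. It is optional, because the mean-based test already kept its error rate near nominal.

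The cost is a sentence in each document. Sample size, visits and data collection are unchanged. The sentence should be in place before any unblinded comparison of the primary endpoint.
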